A Phase II Trial of Neoadjuvant PD 0332991, a Cyclin-Dependent Kinase (Cdk) 4/6 inhibitor, in Combination with Anastrozole in Women with Clinical Stage 2 or 3 Estrogen Receptor Positive and HER2 Negative Breast Cancer

Principal Investigator Signature Page

Principal Investigator:	[name]., Ph.D.	
<hr/> Signature of Investigator		<hr/> Date
<hr/> Printed Name of Investigator		

By my signature, I agree to personally supervise the conduct of this study and to ensure its conduct in compliance with the protocol, informed consent, IRB/HRPO procedures, the Declaration of Helsinki, ICH Good Clinical Practices guidelines, and the applicable parts of the United States Code of Federal Regulations or local regulations governing the conduct of clinical studies.
		

Contact Information

Principal Investigator: [name]., Ph.D.
Washington University School of Medicine
Division of Oncology
[name]
[name]
[contact]
[contact]
E-mail: [contact]

SCHEMA

PIK3CA Wild Type or Mutant Cohorts (Closed as of Amendment #7)

Eligible patients: clinical stage II or III ER+ HER2- breast cancer
with complete resection of tumor as a goal

[figure not shown]
Had Pre-registered to NCI 9170 trial* or this trial# and started the following procedure:

- #1: Tumor biopsy for PIK3CA mutation testing and research
- #2 Cycle 0 treatment¹: Anastrozole 1 mg PO daily Cycle 0 Days 1-28
If premenopausal add: Goserelin 3.6mg SC on Day 1

Endocrine Resistant Cohort

Clinical stage II or III ER+
HER2- breast cancer

Ki67 > 10% on neoadjuvant
endocrine therapy

¹Cycle 0 starts while waiting for the result of PIK3CA analysis

²Cycle length=28 Days

³Biopsy prior to PD0332991 is not required in the endocrine resistant cohort if the patient had a research tumor sample collected at the time of Ki67 analysis while on endocrine therapy

⁴Optional biopsy on Day 15 of subsequent cycles is recommended if C1D15 Ki67 was indeterminate or if not performed.

⁵Cycle 5 duration is 10-12 days and administered in patients whose absolute neutrophil is recovered to $\geq 1.5k/\text{mcL}$ and platelet $\geq 100k/\text{mcL}$ and treatment related AEs to grade 1 or less within 3 weeks after completion of cycle 4. Patients who do not meet this criteria may proceed to surgery in 3-5 weeks post cycle 4 day 21 PD0332991.

[figure not shown]

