IMPACT 2W Ki67	% PEPI 0	RFS (events)
$>10\%$	0/32 (0%)	9/35 (26%)
$\leq 10\%$	21/101 (21%)	13/118 (11%)
P Value	$P=0.004$ (Fisher)	$P=0.008$ (log rank)

In this trial, to avoid futile therapy, we plan to obtain tumor biopsy post 2 weeks of PD 0332991 in combination with anastrozole. Patients whose Day 15 Ki67 $>10\%$ will be considered resistant to the combination therapy. These patients will be recommended alternative therapies such as immediate surgery or neoadjuvant chemotherapy. The pre-PD 0332991 Ki67 will not be used for clinical decision making since PD 0332991 will be added to the treatment regimen. It is, however, important to obtain the pre-PD 0332991 Ki67 since this allows a comparison between anastrozole alone and the combination of anastrozole and PD 0332991 on the degree of Ki67 suppression.

1.9.2 To Assess Tumor Cell Apoptosis on Biopsies Taken Pre-PD 0332991 and Cycle 1 Day 15

We will investigate whether there is an increase in tumor cell apoptosis with the combination of PD 0332991 and anastrozole (or anastrozole in combination with goserelin). Anastrozole 1mg daily dosing reduced estradiol level by 70% by 24 hours and by approximately 80% after 14 days of daily dosing [AstraZeneca, Package Insert], therefore, full estrogen deprivation is expected by 28 days of anastrozole administration. In the case of goserelin, serum estradiol is suppressed to levels similar to those observed in postmenopausal women within 3 weeks

following administration. In addition, only 5% or less of women treated with goserelin, FSH and LH may not be suppressed to follicular phase levels on day 28 post treatment with a single 3.6mg depot injection [AstraZeneca, Package Insert].

1.9.3 To Assess the Degree of Ki67 Suppression before (Pre-PD 0332991) and after PD 0332991 (Cycle 1 Day 15)

The degree of Ki67 suppression following 2-4 weeks of therapy has been associated with the effectiveness of endocrine agents or the combination of endocrine agent with an mTOR inhibitor. In the IMPACT trial, suppression of Ki67 after 2 and 12 weeks was significantly greater with anastrozole than with tamoxifen ($P = 0.004$) which mirrored the result based on RFS in the ATAC trial [100]. These data indicate that Ki67 response early on therapy could potentially be employed as a measurement of treatment efficacy.

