3.4 Eligibility Criteria for the Endocrine Resistant Cohort

3.4.1 Inclusion Criteria

1. Clinical T2-T4c at diagnosis or screening, any N, M0 invasive ER+ (Allred Score at least 3 or > 1% ER positivity) and HER2 negative (0 or 1+ by IHC or FISH negative or equivocal) breast cancer, by AJCC 7th edition clinical staging, with the goal being surgery to completely excise the tumor in the breast and the lymph node.

Note: Patients with invasive breast cancer that is ER pos, HER2 neg or equivocal or DCIS in the contralateral breast are eligible; multi-focal diseases are not excluded. The dominant lesion will be followed per protocol.

2. Ki67 > 10% by central testing at Washington University AMP laboratory from a tumor biopsy performed after at least 2 weeks on neoadjuvant endocrine therapy.

If Ki67 is > 10% by local testing, the Ki67 slide and H&E slide need to be reviewed by the study pathologist to confirm eligibility (discuss with Study Chair). For patients external to Washington University, please contact the Washington University coordinator by email so that a screening ID# can be assigned prior to shipment of the slides.

Note that prior neoadjuvant endocrine therapy could include any endocrine therapy (including aromatase inhibitor, tamoxifen, fulvestrant) alone or in combination, or endocrine therapy in combination with any investigational agent that is not a Cdk 4/6 inhibitor.

3. Female \geq 18 years of age.
4. ECOG performance status of 0, 1 or 2 (Appendix A).
5. Pre- or post-menopausal women are eligible

If premenopausal, patient must be willing to comply with pregnancy requirements laid out in Section 5.5 and agrees with GnRH agonist therapy for ovarian suppression during the study.

6. Adequate organ and marrow function as defined below:
 - a. Leukocytes \geq 3,000/mcL
 - b. Absolute neutrophil count \geq 1,500/mcL
 - c. Platelets \geq 100,000/mcL
 - d. Total bilirubin \leq upper normal institutional limits
 - e. AST(SGOT)/ and ALT(SGPT) \leq 2.5 X institutional upper limit normal
 - f. Creatinine \leq upper normal institutional limits
7. Able to understand and willing to sign an IRB-approved written informed consent document.

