9.1.3 Sample Collection and Schedule in the Neoadjuvant Setting (Endocrine Resistant Cohort)

All sample collection is mandatory.

Correlative Study	Blood / Tumor	Type of Tube	Volume to Collect	Time point	Process at Site?	Temperature Conditions for Storage / Shipping
Tumor for research♣	Core biopsies	2 cores in OCT 2 cores in 10% formalin	14-G core needle	Pre-PD0332991, C1D15, Surgery*	No	Cores in OCT should be immediately frozen; cores in formalin should be stored / shipped at ambient temperature
Plasma for research	Whole blood	EDTA (purple)	10 mL	Pre-PD0332991, C1D15, Surgery	Yes	-80°C
Serum for research	Whole blood	Clot-tube (red)	10 mL	Pre-PD0332991, C1D15, Surgery	Yes	-80°C
Germline DNA for research	Whole blood	EDTA (purple)	10 mL	Pre-PD0332991	No	Ambient, same-day shipment (avoid Friday blood draw)
Whole blood for plasma circulating DNA	Whole blood	Cell-free DNA BCT	10 mL x2	Pre-PD0332991, C1D15, Surgery	No	Ambient, same-day shipment (avoid Friday blood draw)

Pre-PD0332991: C1D1

♣ Tumor collection prior to PD0332991 is not required for the endocrine resistant cohort if the patient had undergone research tumor collection as part of the tumor biopsy for the Ki67 analysis prior to registration to this trial. Consent to research of archival tumor specimens collected prior to and during this trial is required for all patients.

* Additional surgical tumor specimens are required; please refer to instruction 'g' below

Instructions for sample collection and processing:

Note that sample collection/shipment kits are available for the study.

- a: For biopsies at each time point: 4 cores (14 G core needle) will be taken at each time point, with 2 in 10% formalin and 2 freshly frozen in OCT. Care needs to be taken to reduce the ischemic time to as much as possible to less than 30 min.
- b: A repeat biopsy may be needed in consented patients if the first biopsy did not yield enough tumor cells for Ki67.
- c: Samples can be obtained at the time of surgery. Care needs to be taken to reduce the ischemic time to as much as possible to less than 30 minutes.

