- K. Serum chemistry is albumin, alkaline phosphatase, total bilirubin, bicarbonate, BUN, calcium, chloride, creatinine, glucose, potassium, total protein, SGOT/AST, SGPT/ALT, sodium
- L. In premenopausal women only
- N. EKG will be performed at baseline, pre-surgery, and as needed. Surgery may be delayed if QTc prolongation has occurred.
- O. Mammogram and ultrasound of the diseased breast must be completed within 12 weeks prior to registration. Imaging studies must include bidimensional breast tumor measurements, but retrospective measurement is allowed in the study.
- P. C1D15 biopsy and blood draw may be done up to C1D20 for scheduling convenience, although C1D15 is strongly preferred.
- Q. Optional biopsy on C2D15, C3D15, or C4D15 in patients with indeterminate Ki67 on C1D15 biopsy or who missed the C1D15 biopsy.
- R. Research funded. Research blood samples are mandatory except where indicated.
- S. Optional
- T. If counts recover within 3 weeks of the end of C4, re-start PD 0332991 for 10 to 12 doses (C5) (last dose to be the day before surgery).
- U. PKs to be drawn on a day prior to initiation of PD 0332991 (may be C1D1) pre-anastrozole and again 90 minutes post-anastrozole. Other research blood include serum, plasma, whole blood for germline DNA and whole blood for circulating tumor DNA is also collected on C1D1. Details are described in Section 9.1.2. PK samples are not required in the endocrine resistant cohort.
- V. PKs to be drawn pre-dose of both drugs and again 90 minutes post-dose of both drugs. PK samples are not required in the endocrine resistant cohort.
- W. Not required in endocrine resistant cohort if a research biopsy was performed prior to registration or an archival tumor block is available
- Y. Only required in patients who are in Cycle 5.

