15.6 Correlative Studies

Tumor cell apoptotic index: Apoptosis studies based on the TUNEL assay conducted in the context of the IMPACT study showed that the rate of apoptosis actually *declined* after two weeks of anastrozole treatment when the percentage TUNEL positive cells was less than one percent, with an SD of less than one percent [12]. Given the very low background of TUNEL positivity, a modest sized study is sufficient to demonstrate an increase in cell death. We will use the TUNEL assay to assess apoptosis at baseline and in the sample taken on PD 0332991. The TUNEL-positive cells will be counted using the point counting approach used for Ki67 and the apoptosis index will be calculated as the number of positive cells divided by the number of all cells and multiplied by 100.

Steady state levels of estradiol: Steady state levels of estradiol on serially collected serum samples will be examined in premenopausal women to confirm the efficacy of the

anastrozole goserelin therapy in suppressing both ovarian and peripheal estradiol production. The change of estradiol level over time will be described by summary statistics and also compared using 2-way ANOVA for repeated measurement data

Pharmacodynamic markers and markers of tumor cell senescence: The pharmacodynamic effect of PD 0332991 in combination with anastrozole on RB phosphorylation and markers of senescence will be assessed by phosphoproteomics and immunohistochemistry analysis on serial tumor biopsies. The change of RB phosphorylation and senescence markers over time will be described by summary statistics and also compared using 2-way ANOVA for repeated measurement data.

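### Calendar footnote W (10.2) waives the pre-PD 0332991 biopsy in the endocrine resistant cohort more widely than the schema, 9.1.2 and 9.1.3 allow, which puts some exploratory pre-drug tissue at risk

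*Combined protocol and SAP*

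**What the plan says.** Four places state when a patient in the endocrine resistant cohort may skip the biopsy before PD 0332991.

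- Schema, footnote 3: not required "if the patient had a research tumor sample collected at the time of Ki67 analysis while on endocrine therapy".
- Section 9.1.3: not required "if the patient had undergone research tumor collection as part of the tumor biopsy for the Ki67 analysis prior to registration to this trial". The note under the 9.1.2 table gives the same condition for this cohort.
- Section 10.2, footnote W: "Not required in endocrine resistant cohort if a research biopsy was performed prior to registration or an archival tumor block is available".

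Section 9.1.3 makes all sample collection mandatory and sets the tissue format: "4 cores (14 G core needle) will be taken at each time point, with 2 in 10% formalin and 2 freshly frozen in OCT". Its schedule for this cohort has three tumor time points: before PD 0332991, C1D15 and surgery. No pre-endocrine baseline is collected.

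Entry under 3.4.1 requires Ki67 above 10% "from a tumor biopsy performed after at least 2 weeks on neoadjuvant endocrine therapy". Section 1.9.1 explains why the pre-drug sample is wanted: "this allows a comparison between anastrozole alone and the combination of anastrozole and PD 0332991 on the degree of Ki67 suppression". Section 15.6 then relies on serial tissue: "The change of RB phosphorylation and senescence markers over time will be described by summary statistics".

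**The concern.** Footnote W sets no condition on when the earlier tissue was taken, whether the woman was on endocrine therapy at the time, or what format it is in. Read literally, a diagnostic block is enough. The other three places do not allow that.

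The cohort has a single arm, so the on-endocrine pre-drug sample is each woman's own control for the effect of adding PD 0332991. Without it the before/after pair is lost. If a pre-endocrine block took its place, the change to C1D15 would contain the effect of endocrine therapy as well. The objectives at stake are the exploratory ones in 2.3, which are to be assessed separately in this cohort: apoptosis, senescence, pharmacodynamic and resistance markers.

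Two features make the conflict more than cosmetic. Section 11 says that an electronic study calendar drives data collection, so if that calendar was built from 10.2, W is the rule sites will meet. In addition, where the calendar lets earlier samples substitute in the other cohorts (10.1, footnote G), it requires that they were collected to the Section 9 instructions. W carries no such condition.

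**Working it through.** **1. The rules side by side**

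| Place | Tied to the qualifying Ki67 biopsy? | On endocrine therapy? | Archival block sufficient? |
|---|---|---|---|
| Schema, footnote 3 | Yes | Yes, stated | No |
| Notes under 9.1.2 and 9.1.3 | Yes | Yes, through 3.4.1 | No |
| 10.2, footnote W | No | Not required | Yes, any |

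9.1.3 does ask for consent to research on archival specimens, but it does not let them replace the biopsy.

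**2. Who falls between the rules**

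Under 3.4.1 a woman with a local Ki67 above 10% can be confirmed by the study pathologist's review of her Ki67 and H&E slides. She may then have no research cores. The schema and 9.1.3 require her pre-drug biopsy; W waives it if any block exists.

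**3. What does not depend on the sample**

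The primary test compares the C1D15 arrest rate with fixed rates of 5% and 20% (15.3). The plan's design figures reproduce:

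- Early stopping: 0.95^12 = 0.540 at a 5% rate and 0.80^12 = 0.069 at 20% (plan: 54% and 7%).
- Exact two-stage binomial, continuing with at least 1 of 12 and positive with at least 4 of 37: alpha 0.0935 and power 0.902 (plan: 0.1 and 90%).

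None of this uses pre-drug tissue. For Ki67, arrest means 2.7% or less and entry requires more than 10% on endocrine therapy. Every woman is therefore a documented non-arrest before the drug, and the before/after arrest table is protected. The plan does not say that the entry value stands in for C1D1, although it is the natural choice.

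**4. What does depend on it**

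- RB phosphorylation and senescence markers over time (9.4.3, 9.4.4, 15.6).
- Apoptosis, framed in 1.9.2 as pre-PD 0332991 against C1D15. Section 15.6 says baseline against the on-drug sample, but the only pre-drug specimen scheduled in this cohort is the pre-PD 0332991 one.
- Resistance markers, measured on the C1D1 specimen itself (9.4.6, 15.6).

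**5. Illustration of mixing (effect sizes assumed)**

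Suppose endocrine therapy alone lowers a marker by e and PD 0332991 lowers it by a further d. From a pre-endocrine block the apparent drop is 1 − (1 − e)(1 − d). With d = 30%:

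- e = 0: 30%
- e = 20%: 1 − 0.8 × 0.7 = 44%
- e = 40%: 1 − 0.6 × 0.7 = 58%
- e = 60%: 1 − 0.4 × 0.7 = 72%

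With d = 0 the apparent drop is e. For apoptosis the error could run the other way: 1.2.1 and 15.6 report that TUNEL staining fell on anastrozole, so a pre-endocrine comparator could hide a rise caused by PD 0332991.

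**6. Illustration of lost pairs (share assumed)**

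The documents do not give the share of women with no on-endocrine research tissue. If it were 10% to 50% of 37, about 4 to 18 pairs would go, leaving 33 to 19. The standard error of a paired mean change would rise by a factor of √(37/33) = 1.06 to √(37/19) = 1.40. This supposes that all 37 women are enrolled and every other pair is evaluable; only 12 are enrolled if Stage 1 stops the cohort.

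**The case against.** Every woman in this cohort has had a biopsy on endocrine therapy, because 3.4.1 demands it. W's archival block may well mean the block from that biopsy, and 9.1.3 already secures consent to use it. Dates are also on record: 9.1.5 requires collection date and time on each sample, the specimen form repeats them, and the Appendix B worksheet asks when endocrine therapy began. An analyst could therefore recognize a pre-endocrine block. All of this stands, and it limits the harm. It does not remove the conflict, because W does not say which block it means and no analysis section says what to do with an early one.

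A reader might infer that endocrine effects will be credited to PD 0332991. The documents do not support that. W only waives a procedure, and nothing in 9.4 or 15.6 says a pre-endocrine block will be analyzed as the C1D1 sample. Nor do they support the inference that W cancels most of the pre-drug samples, since they give no uptake figure.

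The frozen-tissue loss should not be put down to W alone. Apoptosis is run on FFPE sections and the senescence markers by IHC, and pRB is assessed by IHC as well. Phosphoproteomics is probably the most exposed assay, although the documents do not say which assays use the frozen cores. The schema and 9.1.3 also do not say that earlier research tissue must include frozen cores.

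**Conclusion.** The plan contradicts itself: W is wider than three other statements of the same waiver, and the passages must be reconciled. The consequence is confined to exploratory tissue analyses. For some women the on-endocrine pre-drug sample could be missing, so the pair is lost, or represented only by a pre-endocrine block, so that any contrast using it mixes two treatments. Either outcome is possible rather than certain. How many women are affected is unknown, and the figures in steps 5 and 6 of the working rest on assumed inputs.

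It would be wrong to read this as a threat to the trial's main result. The primary endpoint, the two-stage design and the Ki67 arrest classification stand. It still merits correction while the cohort is enrolling, because tissue not taken before the first PD 0332991 dose cannot be recovered.

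One limit remains after reconciliation. Section 3.4.1 allows any prior endocrine agent, so even an on-endocrine pre-drug sample is not always a sample on anastrozole.

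**What to change.** 1. Give schema footnote 3, the notes under 9.1.2 and 9.1.3, and footnote W one identical waiver condition, tied to tissue from the qualifying Ki67 biopsy taken on endocrine therapy.
2. Decide whether an archival block from that biopsy is acceptable. At present 9.1.3 does not provide for it. If it is accepted, say so in all four places, and note that such a block has no frozen cores, so those women drop out of assays that need frozen tissue.
3. In 15.6, compare the recorded collection date with the recorded endocrine start date, and exclude pre-endocrine tissue from every contrast before and after PD 0332991. Report the number of valid pairs for each marker.

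The cost is a wording change in up to four places and one analysis rule. No new data field is needed, and no biopsy beyond those the schema and 9.1.3 already require. The downside is slightly fewer pairs in the exploratory analyses.

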10.3 Post Surgery Treatment Calendar

Patients who had a Ki67<10% on the neoadjuvant C1D15 tumor biopsy in the endocrine resistant cohort (before or after activation of Amendment #7) and the 26 patients who enrolled initially to the main trial (PIK3CA WT or mutant cohort) who required PD 0332991 to achieve complete cell cycle arrest have the option of restarting PD 0332991 in combination with anastrozole for adjuvant treatment (23 cycles after surgery). These patients will need to be consented and screened for the adjuvant portion of the study, and may only begin treatment with adjuvant PD 0332991 if they meet the eligibility criteria in Section 3.4 and if they have provided informed consent.

PD 0332991 should be re-started at least 4 weeks after the completion of chemotherapy and radiation therapy if these treatments were planned. Anastrozole may be started earlier while the patient receives radiation therapy if desired. After completion of PD 0332991, patients should continue standard of care hormonal therapy (for example anastrozole) to complete at least 5 years of therapy. Further therapy after that is at the discretion of treating physician.

	Screening	Adjuvant Cycles 1-2		Adjuvant Cycles 3 to 23	End of C23 or early termination	Follow up
Day of cycle	-30 to 0	D1 +/- 3 days	D14 +/- 3 days	D1 +/- 7 days (C3, 6, 9, 12, 15, 18, 21)	4 weeks	+/- 8 weeks
TREATMENT						
Endocrine Therapy ^A		Daily				
PD 0332991		Days 1-21 each cycle				
CLINICAL ASSESSMENT						
Informed consent	X					
Concomitant medication	X	X		X	X	
H&P, PS	X	X		X	X	
Adverse event assessment	X	X	X	X	X	X
ECG	X					
Disease monitoring ^B	X			Per standard of care		
CBC+ differential	X	X	X	X	X	X
Serum chemistry ^C	X	X		X	X	X
Serum/urine pregnancy test ^G	X	X		X	X	
Drug compliance assessment ^D		X		X	X	
Research blood ^E		X		X (C12 only)	X	X

- A. Premenopausal women requires goserelin
- B. Disease monitoring is per standard of care.
- C. Serum chemistry is albumin, alkaline phosphatase, total bilirubin, bicarbonate, BUN, calcium, chloride, creatinine, glucose, potassium, total protein, SGOT/AST, SGPT/ALT, sodium.
- D. Patients will keep a pill diary (Appendix D).
- E. Research blood includes the collection of plasma, serum and whole blood for cfDNA.
- F. For patients who did not receive adjuvant PD 0332991 the follow up is yearly for 5 years post surgery or until recurrence whichever comes first.
- G. In premenopausal women only.

